Treatment of mild cognitive impairment with transcutaneous vagal nerve stimulation

NCT03359902

1/1/2018

C6.1 Data analytic strategy [name] (Co-I, biostatistician) will conduct the statistical analyses, which will be performed using statistical software, R or SAS. First, standard summary statistics will be provided for all measures (including behavioral and demographic [e.g., sex] measures, volumetrics from T1 weighted images, white matter integrity on DTI and white matter hyperintensities from FLAIR, and baseline neuropsychological test performance) by treatment (sham or active during the first stimulus session). Second, hypotheses will be tested with formal inferential techniques. Third, exploratory analysis for baseline neuropsychological test performance, brain regional volume, and other regional indices from DTI for predicting treatment response will be conducted. We will adjust for multiple comparisons by controlling the false discovery rate and determine statistical significance for each aim. The crossover design will increase the precision, where each subject serves as his or her own control and within subject comparison can be used. The increased power with greater precision to estimate the treatment differences reduces the necessary sample size. Despite this advantage, a potential problem in a crossover design is that carryover effects may bias the direct treatment effects. To account for the potential carryover effects, we will consider the following mixed-effect model. Let y_{ijk} denote the memory score measured at time period k from the j th subject in sequence i ,

$$y_{ijk} = \mu + \beta_{j(i)} + \gamma_k + \tau_{d(i,k)} + \lambda_{c(i,k)} + \epsilon_{ijk},$$

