where i =sequence (tVNS-sham or sham-tVNS), j =subject, k =period, μ is the overall mean, δ_i is the fixed effect of sequence i , $\beta_{j(i)}$ is the random effect for patient j with sequence i , γ_k is the effect of period k , $\tau_{d(i,k)}$ is the direct effect of the treatment applied during period k in sequence i , $\lambda_{c(i,k)}$ is the carryover effect of the treatment applied during period k in sequence i , and ϵ_{ijk} is the random error effect. Note that there is randomization of the subjects to the sequences. If the outcome measures do not follow a normal distribution, certain transformation, e.g., a Box-Cox transformation, will be applied before modeling. With this mixed-effect model, various hypotheses on the treatment effects, period effects and carryover effects can be separated and tested. If the carryover effect is not significant between the two sequences, then the data from two periods can be combined and analyzed. In the case that the carryover effect is significant, the overall conclusion about the treatment effect would be in question, however, the data from the first time period can still be used in testing for treatment effects because there would be no carryover from any previous applications of the treatments. Further, we will conduct secondary analysis for investigating the effect of tVNS on the other cognitive domains including language (phonemic and semantic fluency) and executive functions. To identify the factors that mediate the effects of tVNS, i.e., testing the hypothesis in Aim 2, the memory scores will be regressed on the selected factors, such as baseline memory performance (flat learning curve, poor free recall, reduced recognition memory; reduced working memory and poor retrieval with intact recognition), and hippocampal/entorhinal cortex volume (normalized by intracranial volume). Important covariates such as sex, age and education will be adjusted in the regression model if they relate significantly to the outcome variables. Variable selection can be conducted for the model under the standard Bayesian or frequentist framework. For example, a L1-penalty⁴⁹ might be used in variable selection under the frequentist framework. In addition to the plain linear regression model, the generalized additive model⁵⁰ will also be tried for the problem, which is expected to fit the data better and have a better power to detect the factors that are truly associated with the effects of tVNS.

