C6.2 Power and sample size considerations The enrollment sample of 60 participants is intended to provide data on the impact of tVNS on the cognitive performance in participants with MCI and predictors of improvement with treatment including brain volume changes associated with AD pathology. Further, these data will be used to indicate feasibility of a larger trial and to provide descriptive estimates of acute effects. To get a rough idea for the effectiveness of the trial, we made the following calculation. Assuming $\alpha = 0.05$, two-sided test, and 60 participants in total. If the carryover effect is negligible, we will have 90% power to detect an effect size of 0.604 for memory improvement in hypothesis 1 in aim 1 based on within subject comparisons. In the case that the carryover effect is significant and we use the first period data only (similar as in a parallel design), we will have 90% power to detect an effect size of $d=0.854$ for aim 1. For the regression analysis in predicting treatment response in aim 2), we will have 90% power to detect a factor that has a marginal correlation of $r=0.43$ with the response variable.

Overall, our methodology and analyses offer a comprehensive approach to understanding the mechanism of action of tVNS as a potential enhancer of cognition affected by decline in the continuum of AD. Our strategy should establish feasibility and our personalized medicine approach will allow us to interrogate treatment responsiveness and examine predictors of said responsiveness. Subsequent larger scale clinical trials including biomarkers such as amyloid imaging, CSF tau, and genetic subtypes (APOE) and longitudinal evaluation of sustainability of effects and whether decline in functional status can be achieved will follow.

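### In Aim 2, sex, age and education are adjusted for only if significant in the trial's own data; this can raise the false-positive rate for a predictor from 5% to about 10–12%, or hardly at all, depending on correlations the plan does not give

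*SAP*

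**What the plan says.** SAP C6.1 describes the Aim 2 analysis as a regression: "the memory scores will be regressed on the selected factors". The factors include patterns of baseline memory impairment and "hippocampal/entorhinal cortex volume (normalized by intracranial volume").

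On covariates it says that sex, age and education, which it calls important, "will be adjusted in the regression model if they relate significantly to the outcome variables". It names no significance level, does not say whether each covariate is tested alone or with the factor in the model, and points to no outside data. The natural reading is a test in the trial's own participants.

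The same section leaves variable selection open (an L1 penalty is the example), adds a generalized additive model as a further option, and sets the multiplicity rule: "We will adjust for multiple comparisons by controlling the false discovery rate and determine statistical significance for each aim".

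SAP C6.2 gives the design figures: "Assuming $\alpha = 0.05$, two-sided test, and 60 participants in total". For Aim 2 it states: "we will have 90% power to detect a factor that has a marginal correlation of $r=0.43$ with the response variable".

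**The concern.** Whether a covariate confounds a factor depends on its relation to both the factor and the outcome. Its p-value against the outcome in one sample of 60 is a poor guide to that. A modest but real confounder will often miss significance and be dropped, and the factor is then credited with part of its effect.

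The exposed factors are the subject of the named Aim 2 hypotheses (Protocol section 6). In participants aged 60 to 89 (Protocol C2.2), hippocampal or entorhinal volume and baseline memory could plausibly vary with age and education. If a factor's p-value is too small for this reason, the false discovery rate step takes that p-value as its input and cannot correct it. The rule also means that the adjustment set is settled only after the outcomes have been seen.

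**Working it through.** **The plan's own Aim 2 figure.** Inputs from SAP C6.2: r = 0.43, N = 60, two-sided α = 0.05. Fisher z power is Φ(atanh(r)·√(N−3) − 1.960) = Φ(0.4599 × √57 − 1.960) = Φ(1.512) = 93.5%, not 90%. For 90% power the detectable r is tanh(3.2415/√57) = tanh(0.429) = 0.405. The stated 0.43 therefore looks like a Fisher z value reported as r. That error is conservative and does not bear on this point.

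**How often a covariate is dropped.** In simulation at n = 60 and two-sided 5%, a true outcome correlation of 0.20 is significant in about 34% of trials and 0.25 in about 49–50%. The covariate is left out about 66% and 50% of the time. Three independent covariates at 0.20 all enter in only about 0.34³ = 3.9% of trials.

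**False-positive rate of a factor with no effect given the covariates.** The documents give no correlation of sex, age or education with any factor or outcome, so all of these are assumed. Each covariate is tested alone at 0.05, the significant ones are kept, and the factor is then tested at 0.05. Covariates are independent and simulated as continuous. With a the correlation with the factor and c with the outcome, the factor–outcome correlation due only to confounding is Σac.

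| Confounders | a | c | Σac | Rate under the rule |
|---|---|---|---|---|
| One | 0.3 | 0.2 | 0.06 | 5.4% |
| One | 0.5 | 0.3 | 0.15 | 5.8% |
| One | 0.7 | 0.3 | 0.21 | 6.4% |
| Three | 0.4/0.3/0.3 | 0 | 0 | 4.3% |
| Three, one of opposite sign | 0.3 each | 0.2 each | 0.06 | 5.3% |
| Three | 0.1 each | 0.2 each | 0.06 | 5.7% |
| Three | 0.2 each | 0.2 each | 0.12 | 6.9% |
| Three, uneven | 0.4/0.1/0.1 | 0.2 each | 0.12 | 6.9% |
| Three | 0.4/0.3/0.3 | 0.4 each | 0.40 | 7.9% |
| Three | 0.3 each | 0.2 each | 0.18 | 9.3–9.7% |
| Three | 0.4/0.3/0.3 | 0.2 each | 0.20 | 9.7–10.4% |
| Three | 0.5/0.3/0.3 | 0.25 each | 0.275 | 11.6% |

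Two figures in a cell come from separate runs of 10,000 to 20,000 trials. With 20,000 trials the standard error at 10% is √(0.10 × 0.90/20,000) = 0.2 points. Always adjusting gave 4.6–5.3% in every setting, within simulation error of 5%.

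A single confounder does little harm because, when it is dropped, its sample correlation with the outcome is usually small. With several, the small omitted parts add up. The 7.9% row shows the reverse: at c = 0.4 a covariate is significant about 90% of the time, so most of the confounding is removed.

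**The other reading of the test.** If each covariate is tested with the factor in the model, which the SAP does not rule out, the rates are higher. One confounder gives 7.2% at a/c = 0.3/0.2, 9.5% at 0.4/0.3 and 13.0% at 0.5/0.3. Three give 10.1% at 0.2/0.2 and 15.5% at 0.3/0.2.

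**Power cost of always adjusting.** With three covariates the Fisher z term uses √(60−3−3) = √54. At a partial r of 0.43: Φ(0.4599 × √54 − 1.960) = Φ(1.420) = 92.2%, against 93.5%. At r = 0.405: Φ(0.4296 × √54 − 1.960) = Φ(1.197) = 88.4%, against 90.0%.

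**The case against.** A reader might infer that the rule as such roughly doubles the false-positive rate. The documents do not support that. Doubling under univariable testing needs several independent confounders that all act in the same direction and are fairly strongly tied to the factor. At 0.4/0.3/0.3 they already explain 0.16 + 0.09 + 0.09 = 34% of the factor's variance, and at 0.5/0.3/0.3 they explain 43%. More extreme inputs give more extreme answers: 13.1% at 0.4 each with 0.2, and 22.0% at 0.5 each with 0.25, where the covariates explain 48% and 75% of the factor. The inputs set the result. This objection stands, and the size has to be stated as a range.

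The plan may weaken some of the assumed links. Dividing by intracranial volume should reduce a link between volume and sex through head size. Impairment at entry is judged against demographic and educational norms (Protocol C2.2), and if the baseline memory factors use normed scores, their links to age and education shrink. Neither step is an adjustment for all three covariates.

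The outcome is also unsettled. C6.1 regresses memory scores, while C6.2 speaks of predicting treatment response. If the outcome is the within-person tVNS-minus-sham difference, covariate effects on the level of memory cancel, and only their effect on the benefit of tVNS remains. Inflation would then be smaller. This stands as a limit on the size.

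Finally, C6.1 labels prediction of response as exploratory, although it also speaks of testing the Aim 2 hypothesis. The open choice of selection method and model leaves flexibility that fixing three covariates will not remove. Both points limit the concern. Neither removes it, because nothing else in the plan corrects the affected p-values.

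**Conclusion.** The concern holds in conditional form. The SAP states a data-driven rule for confounder adjustment. At n = 60 the rule omits a covariate with a true outcome correlation of 0.20 to 0.25 about 50–66% of the time.

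Under univariable testing at 5%, the false-positive rate for a factor that shares these confounders lies between little change and about 10–12%. The low end, about 4–7%, covers one confounder and weak, uneven or mixed-sign correlations. The high end needs three independent confounders acting in the same direction, with factor correlations from 0.3 each up to 0.5/0.3/0.3 and outcome correlations of 0.20 to 0.25.

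All of these correlations are assumed. Testing covariates jointly with the factor would give higher rates, and a within-person difference as outcome would give lower ones. Confidence in the direction is good; confidence in the size is moderate. The case for change rests on the low cost of removing the problem in every setting, and does not need any one inflation figure to be right.

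**What to change.** Replace the conditional clause in SAP C6.1 with: *Age, sex and education are included in every Aim 2 regression regardless of their significance.* Add that these three are exempt from any variable selection or L1 penalty; otherwise the selection step could drop them again.

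The cost is two sentences in the SAP and three degrees of freedom, with no new data and no more participants. If the covariates turn out to be irrelevant, the loss is about 1–2 points of power (93.5% to 92.2% at r = 0.43, still above the planned 90%). The change secures the covariate set only. It does not settle the choice between the linear and the additive model, or how the other factors are selected.

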Hypothesis 2: Research has demonstrated that neurodegeneration of medial temporal structures is the best antecedent MRI marker of imminent conversion to AD, with decreased hippocampal volume (left > right) being the most robust. Since the hippocampus receives direct input from the NTS as well as norepinephrine from the LC, those participants with MRI evidence of degeneration of the hippocampus/entorhinal cortex (its direct path connections (using diffusion tensor imaging [DTI])) *will improve during tVNS and the degree of improvement may be related to the degree of atrophy.*

Hypothesis 3: Those patients with MCI who have baseline memory impairment including reduced working memory and poor retrieval with intact recognition will improve with tVNS.

Hypothesis 4: Since norepinephrine is important for the function of the prefrontal-executive systems, patients with deterioration of prefrontal cortex as evidenced by atrophy and/or white matter integrity loss will show improvements in retrieval and working memory with tVNS as assessed by cognitive testing (digit span, free retrieval memory after a delay) and *the degree of improvement may be related to the degree of structural abnormality.*

7. Research Plan: Experimental design The design of the study is a hybrid, crossover trial structure with randomized and counterbalanced order of tVNS or sham tVNS (to control for ability to detect stimulation/placebo effects) administration (see *table 1 for basic design elements*). This will allow us the benefits of both a parallel and crossover design in that we will have equal numbers of subjects who have received sham or tVNS at time point 1 allowing a between subject analysis, while also allowing a crossover analysis. This design also enables the assessment of potential carryover and practice effects. Participants will attend four contact periods: 1) consent, inclusion screening, MRI eligibility and screening, structured history interview; 2) MRI scan; 3) and 4) stimulus sessions separated by at least 7 days, each consisting of the experimental protocol described below.

Intervention	Predictor	Outcome
tVNS versus sham stimulation (counterbalanced)	Baseline/sham cognitive performance	Cognitive performance - Memory, executive function
	Hippocampal/entorhinal volume	
	White matter variables	

Table 1: Intervention, predictors, and outcomes

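### The Aim 2 models name no sequence or period term, so a practice gain between sessions could cost precision that one forced order term would recover

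*SAP*

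**What the plan says.** Protocol section 7 (Experimental design) describes a crossover with "randomized and counterbalanced order of tVNS or sham tVNS" and remarks: "This design also enables the assessment of potential carryover and practice effects". Section C3.1 has the behavioural testing done twice, at least a week apart. The C5.5 battery includes word-list, story and paired-associate learning, and no alternate forms are mentioned.

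SAP C6.1 sets out a mixed model for the memory score with subject, period, treatment and carryover effects. For Aim 2 it moves to a regression of memory scores on baseline memory profile and hippocampal or entorhinal volume. Sex, age and education are given as examples of covariates, to be adjusted for only when significantly related to the outcome. Variable selection, for example by an L1 penalty, is allowed, and a generalized additive model is to be tried "In addition to the plain linear regression model". Sequence and period are not mentioned for these models.

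The Aim 2 outcome appears as memory scores and treatment response in C6.1 and as the response variable in C6.2. It is nowhere defined as a tVNS-minus-sham difference. Protocol Table 1 lists baseline or sham cognitive performance among the predictors. For Aim 2, C6.2 states: "we will have 90% power to detect a factor that has a marginal correlation of $r=0.43$ with the response variable".

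**The concern.** The plan foresees practice effects and models period for Aim 1, then names no control for it in the analysis of who responds. Counterbalancing cancels a common practice gain from the mean tVNS-minus-sham difference but not from the spread of individual differences. Participants who had sham first look like better responders, and those who had tVNS first look like worse ones, purely because of order.

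That noise comes from a known, randomised factor and can be removed. Left in, it widens the standard error of every predictor of response in a study of 60. If the sham-session score is itself a predictor, order acts on both sides of the regression, and the result is bias as well as noise.

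**Working it through.** **Inputs from the SAP (C6.2).** Two-sided alpha 0.05, N = 60 ("two-sided test, and 60 participants in total"), r = 0.43. From protocol section 7: equal numbers per order, taken as 30 and 30.

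**Assumed, because the documents give neither.** Practice gain g of 0.2, 0.5 or 0.8 session SD; between-session correlation rho of 0, 0.5 or 0.7, with equal SD in both sessions.

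**1. The plan's own figure.** With Fisher's z, power = Phi(atanh(r) × sqrt(N - 3) - 1.960). At r = 0.43 and N = 60 this is 93.5%, not 90%; a noncentral t calculation gives 95.2%. The correlation with 90% power is 0.405 on Fisher's z, and its untransformed z value is 0.429, which may be the source of 0.43. The stated figure is therefore conservative. That is a separate matter from this point.

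**2. What the gain does to the response.** Let D be tVNS minus sham.
- tVNS first: D = individual response - g.
- Sham first: D = individual response + g.
- With equal sequences, and in session-SD units, Var(D) = 2(1 - rho) + g².

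**3. Effect on correlation and power.** Suppose a factor correlates 0.43 with the order-adjusted response. Without an order term the correlation becomes 0.43 / sqrt(1 + g²/(2(1 - rho))).

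Example, rho = 0.7 and g = 0.5: 0.43 / sqrt(1 + 0.25/0.6) = 0.361. Then atanh(0.361) × sqrt(57) = 2.856, less 1.960 is 0.896, and power is 81.5%.

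| g (SD) | rho = 0 | rho = 0.5 | rho = 0.7 |
|---|---|---|---|
| 0.2 | r 0.426, 93.0% | r 0.422, 92.4% | r 0.416, 91.7% |
| 0.5 | r 0.405, 90.1% | r 0.385, 86.5% | r 0.361, 81.5% |
| 0.8 | r 0.374, 84.4% | r 0.336, 75.1% | r 0.299, 64.4% |

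With sequence in the model, one further degree of freedom is spent: atanh(0.43) × sqrt(56) - 1.960 = 1.48, or 93.1%, whatever the size of a common gain. If there is no practice gain at all, the term costs 93.5 - 93.1 = 0.4 points.

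**4. Slope or correlation?** In simulation (20,000 trials per setting), with a gain equal to one within-sequence SD of D, the mean unadjusted slope was 0.428 against a true 0.43. Its standard error was 0.180, against 0.120 with the order term. For predictors measured independently of the randomised order, the loss is in precision, not in the slope.

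**5. Sham-session score as predictor.** In tVNS-first participants sham is the second session, so the sham score carries +g and D carries -g. In sham-first participants the sham score carries 0 and D carries +g. About their means these are (+g/2, -g) and (-g/2, +g), so order adds a covariance of -g²/2: -0.02, -0.125 and -0.32 at g = 0.2, 0.5 and 0.8. Poorer sham performers would appear to gain more, a pattern easily read as support for Aim 2 Hypotheses 1 and 3.

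**The case against.** The strongest reply concerns the power statement. A reader might infer from the table that the stated Aim 2 power is not delivered. The documents do not support that. C6.2 refers to a marginal correlation with the response variable, and such a correlation is with the response as analysed, so any order noise is already in it. The table starts instead from a correlation of 0.43 with the order-adjusted response. Even on that basis there is slack. Power drops below 90% only when r falls below 0.405, that is, when g exceeds about 0.36 × sqrt(2(1 - rho)): 0.28 SD at rho 0.7, 0.36 SD at rho 0.5 and 0.51 SD at rho 0. The plan's Aim 1 figures ("we will have 90% power to detect an effect size of 0.604 for memory improvement" and "we will have 90% power to detect an effect size of $d=0.854$ for aim 1") fit rho = 0, since 0.854/sqrt(2) = 0.604. This objection stands.

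A reader might also infer that every predictor's effect is pulled toward zero. Step 4 shows that this is not so for baseline and MRI predictors.

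Nor do the documents exclude order. The covariates are given as examples. At g = 0.5 and rho = 0.7, order would correlate 0.645/1.190 = 0.54 with D, so it would probably pass the significance rule if it were considered. What remains is that the plan does not commit to considering it, and both that rule and variable selection could leave it out.

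The opposite-sign mechanism also depends on a difference response that the SAP never defines. Under the first-period fallback in C6.1 there is no between-session gain. Finally, C6.1 calls the prediction of response exploratory and C6.2 calls its calculation rough. These points limit the weight of the concern but do not remove it.

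**Conclusion.** The point holds as a gap in specification with a cheap remedy. It is not an error in the stated power. If the response is the tVNS-minus-sham difference, a common practice gain adds avoidable variance. At rho of 0.5 to 0.7, the loss against about 93% power with an order term is about 1 point at a gain of 0.2 SD, 7 to 12 points at 0.5 SD and 18 to 29 points at 0.8 SD. The true size is unknown, because the documents give neither the practice gain nor the between-session correlation, and it may be trivial. Slopes for baseline and MRI predictors are not biased. Bias from this source arises only if a sham-session score is used as a predictor, and Table 1 leaves that open.

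**What to change.** In C6.1, define the Aim 2 response as the tVNS-minus-sham difference for each participant. State that sequence (tVNS first or sham first) is included in every linear, penalised and generalized additive model of that response, without penalty, outside variable selection and whether or not it is significant. Equivalently, keep the Aim 1 mixed model with its period effect and add predictor-by-treatment terms. If only first-period data are used, sequence coincides with treatment, so the model needs treatment and predictor-by-treatment terms to address response.

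State also whether the sham predictor in Table 1 is a sham-session score. The sequence term removes the -g²/2 component but not ordinary regression to the mean, so a measure taken before the stimulation sessions is the safer predictor.

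The cost is one degree of freedom, about 0.4 points of power if there is no practice gain, and a sentence or two in the SAP. No new data are needed.

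### SAP C6.2: with 60 participants, 90% power for a single marginal correlation is reached at r of about 0.405, not the stated 0.43 (a minor, conservative error)

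*SAP*

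**What the plan says.** SAP section C6.2 sets out its inputs once for all the power figures: alpha 0.05, "two-sided test, and 60 participants in total". It then gives three results, each at 90% power.

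- Aim 1, crossover comparison: "we will have 90% power to detect an effect size of 0.604 for memory improvement in hypothesis 1 in aim 1".
- Aim 1, first period only: "we will have 90% power to detect an effect size of $d=0.854$ for aim 1".
- Aim 2, regression for treatment response: "we will have 90% power to detect a factor that has a marginal correlation of $r=0.43$ with the response variable".

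The section presents these as a rough guide. It mentions no dropout allowance, no stricter alpha and no covariate adjustment in the calculations. SAP section C6.1 describes the Aim 2 analysis itself: "the memory scores will be regressed on the selected factors, such as baseline memory performance", and further, "Important covariates such as sex, age and education will be adjusted in the regression model" if they relate significantly to the outcome.

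**The concern.** A power statement for a marginal correlation has three inputs (sample size, alpha and power), and C6.2 gives all three. The detectable correlation then follows by a standard formula, and the result is not 0.43. The two Aim 1 figures beside it agree with a direct calculation to within 0.003. The Aim 2 figure is off by 0.025, which is too much for rounding.

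This is the only power figure given for Aim 2. C6.2 also says that the data will be used to indicate the feasibility of a larger trial, so later planners may reuse the number. If they do, they should know which correlation goes with which power.

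**Working it through.** **Inputs.** N = 60, two-sided alpha 0.05 and power 90% (SAP C6.2). Equal numbers on sham and tVNS at the first time point, so 30 per sequence (Protocol section 7). Normal quantiles 1.960 and 1.282, with sum 3.2415 before rounding.

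**Step 1. The plan's Aim 1 figures.**

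- First period only, two-sample t test, 30 against 30. The noncentral t calculation gives 90% power at d = 0.851. At the stated 0.854, the noncentrality is 0.854 × sqrt(30/2) = 3.31 and power is 90.2%. This reproduces.
- Crossover, 60 participants, 58 degrees of freedom, effect in units of the residual within-subject SD, so that the SD of a paired difference is sqrt(2) times larger. The calculation gives 90% power at 0.602. At the stated 0.604, the noncentrality is 0.604 × sqrt(60)/sqrt(2) = 3.31 and power is 90.2%. This reproduces.

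**Step 2. The Aim 2 figure as a single marginal correlation.**

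- Fisher z needed for 90% power: 3.2415 / sqrt(60 − 3) = 3.2415 / 7.550 = 0.4293.
- Back-transformed: r = tanh(0.4293) = 0.4048, or 0.405.
- The exact bivariate-normal test gives r = 0.402.

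**Step 3. Power at the stated r = 0.43.**

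- atanh(0.43) = 0.4599, and 0.4599 × 7.550 = 3.472.
- Power = Φ(3.472 − 1.960) = Φ(1.512) = 93.5%.
- The exact calculation gives 93.8%, and a simulation of the t test agrees.

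**Step 4. The sample size for which 0.43 is the 90% value.**

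- N = (3.2415 / 0.4599)² + 3 = 52.7. By Fisher z, 53 participants give 90.2% and 52 give 89.6%.
- By the exact calculation, 52 give 90.2% and 51 give 89.6%.

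**Step 5. Possible sources of 0.43.**

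| Calculation at N = 60 | Value at 90% power |
|---|---|
| Fisher z left untransformed | 0.429 |
| One-factor regression, fixed predictor | 0.392 |
| Partial correlation, 3 covariates: tanh(3.2415/sqrt(54)) | 0.415 |
| Partial correlation, 6 other terms: tanh(3.2415/sqrt(51)) | 0.425 |
| Partial correlation, 7 other terms: tanh(3.2415/sqrt(50)) | 0.429 |
| Partial correlation, 8 other terms: tanh(3.2415/sqrt(49)) | 0.433 |

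Two rows round to 0.43: a Fisher z printed without back-transformation, and a partial correlation adjusted for seven other terms. An alpha of about 0.028 at N = 60 would also give 0.43. C6.2 describes none of these.

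**The case against.** The strongest defence is that C6.2 introduces the figure as part of a regression analysis, and C6.1 lists many terms: several baseline memory features, hippocampal/entorhinal volume, and sex, age and education. That is eight or nine predictors on a plain count. One tested factor with seven others gives a partial correlation of 0.429, so a model of about that size can yield 0.43. This part stands: regression cannot be ruled out as the source. It does not rescue the sentence, because C6.2 calls the correlation marginal and states no adjustment, and C6.1 leaves the factor list open and makes the covariates conditional.

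A second defence is that 90% power to detect 0.43 is true in the sense of at least 90%, that the calculation is described as rough, and that N = 60 is given first rather than derived from r. These points settle the severity: nothing is put at risk. But the neighbouring figures sit at the 90% threshold (90.2% each), so a reader will take 0.43 in the same way.

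Three stronger inferences are tempting, and the documents do not support them.

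- *The three power figures are wrong because they ignore false discovery rate control.* C6.1 does say "We will adjust for multiple comparisons by controlling the false discovery rate and determine statistical significance for each aim", but C6.2 states its alpha of 0.05 openly. The documents give neither the FDR level nor the number of tests, so no adjusted power can be derived. Under assumed conditions (Benjamini-Hochberg at 5%, 4 to 7 tests, r = 0.43, correlation 0.5 among true factors, null factors independent), power per true factor runs from about 79 to 85% with one true factor to about 93% if all are true. That spread reflects the assumptions and does not show an error in C6.2.
- *0.604 and 0.854 conflict.* They do not. Their ratio is sqrt(2), as expected if the first is in residual within-subject SD units, and C6.2 ties it to within-subject comparisons.
- *The SAP printed a Fisher z by mistake.* This is plausible but not shown, given the partial-correlation alternative.

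**Conclusion.** The stated r = 0.43 is not the 90% value for a single marginal correlation on C6.2's own inputs. That value is 0.405 (Fisher z), or about 0.40 exactly. Power at 0.43 is about 93.5 to 93.8%, so the statement understates single-test power by about 3.5 points.

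This is minor and conservative. A reader might infer that Aim 2 is underpowered or that the sample size needs revisiting. On a single-test basis the opposite holds, since 60 participants can detect a slightly smaller correlation than the plan claims. Neither the sample size nor the analysis depends on the figure.

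The conclusion rests on taking the sentence as written: one factor, a marginal correlation, all 60 participants analysed, two-sided alpha 0.05. If a partial correlation was intended, the number may be right and the description is what needs correcting. The 0.604 and 0.854 figures are sound.

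**What to change.** Make one of these changes in C6.2, with no change in N:

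- keep r = 0.43 and state its single-test power as about 93 to 94%; or
- replace r = 0.43 with r = 0.405 at 90% power; or
- if a multi-predictor calculation was intended, replace *marginal* with *partial* and state the number of covariates assumed.

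Two optional clarifications could go in at the same time. One is to label the three figures as per-test, before FDR adjustment. The other is to name the SD behind 0.604: if it is the residual within-subject SD, the figure equals 0.604/sqrt(2) = 0.427 SD of the paired difference. Neither corrects an error.

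The cost is one sentence of text. Sample size, design and analysis stay as they are.
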